#### 5.2.2 Secondary Objectives

Evaluate the impact of a fourth dose on:

1. Symptomatic COVID 19 infection
2. COVID 19 infection requiring hospitalization
3. Antibody levels including IgG, IgA, IgM, binding and neutralizing activity and the avidity of the antibodies.

[figure not shown]
### 5.3 Schedule of Events

Visit number		1	2	3	4	5	6
Time point ( $\pm$ 2 week)	Enrollment	Month 1	Month 2	Month 3	Month 4	Month 5	Month 6
Informed Consent	X						
Inclusion/Exclusion Criteria	X						
Demographics and Medical History	X						
Blood samples*	X	X	X	X	X	X	X
Nasal and mouth Swab**	X	X	X	X	X	X	X
Questionnaire	X	X	X	X	X	X	X
Adverse events	X	X	X	X	X	X	X

\* Antibody levels including IgG, IgA, IgM, binding and neutralizing activity and the avidity of the antibodies. Serum separation and freezing at each site. Only at Soroka medical blood will be drawn for PBMC testing in addition to antibodies testing.

\*\* Antibody levels including IgG, IgA, IgM

## 5.4 Flow chart

Subjects in the control group who are vaccinated after inclusion in the study with a fourth dose will be switched to the vaccinated arm and followed from that point as boosted.

## 5.5 Study Population

The study population will be screened at each participating medical center

The study population will be enrolled according to the following inclusion and exclusion criteria.

### 5.5.1 Inclusion Criteria

1. Able to provide written informed consent.
2. Healthcare worker in one of the Clalit Health Services medical centers and is at least 18 years of age.
3. Completed three doses of BNT162b2 according to MOH guidelines.
4. Third dose was given at least 4 months prior to enrollment.

### 5.5.2 Exclusion Criteria

1. History of COVID-19 infection.
2. History of being treated or is currently being treated for any type of Malignancies or other co-morbid conditions that may result in protocol non-compliance.
3. Currently or in the past three months was treated with any type of Immune suppression medication (including chemotherapy, immunomodulatory drugs, biological agents that affect the immune system, any immunosuppressive drug such as corticosteroids).

4. Received in the past 4 months monoclonal antibodies of any type.

#### **5.5.3 Withdrawal/Discontinuation Criteria**

All subjects should be encouraged to remain in the study through the entire follow up. However, if a subject decides to discontinue study participation, the reason for discontinuation must be recorded in the medical record and the Case Report Form (CRF). Subjects who discontinue participation prematurely will be included in the analysis of results (as appropriate) but they will not be replaced in the enrollment of total study subjects.

Every attempt must be made to have all subjects complete the follow up visit schedule. A subject will not be considered lost-to-follow up unless all efforts to obtain compliance are unsuccessful.

Discontinuation in the study will be if the antibody result at enrollment visit shows the participant already had the disease.

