## 2 Protocol Summary

OBJECTIVE	
Primary Objective  Examine the protection against any type of COVID-19 infection as confirmed by PCR testing or positive serology for N antigen during the follow up period.
 
Secondary Objectives  Evaluate the impact of a fourth dose on:
 
 
1. Symptomatic COVID 19 infection
 
2. COVID 19 infection requiring hospitalization
 
3. Antibody levels including IgG, IgA, IgM, binding and neutralizing activity and the avidity of the antibodies.
 

STUDY DESIGN	Prospective observational registry
OUTCOMES	
Primary Outcome  COVID-19 infection as confirmed by PCR testing or positive serology for N antigen during the follow up period. We hypothesize that booster of BNT162b2 vaccine in healthcare workers (HCW) will lower the rates of the COVID-19 infection as compared to HCW choosing not to receive the second booster.
 
Secondary Outcomes
 
 
1. Symptomatic COVID 19 infection
 
2. COVID 19 infection requiring hospitalization
 
3. Levels of binding and neutralizing activity and avidity of the antibodies
 
4. Composite endpoint of serious adverse events during 14 days following the booster vaccination
 

SAMPLE SIZE CONSIDERATIONS	
We aim to enroll up to 1000 subjects. The following assumptions were used to estimate the power of the analysis.
 
 
• The proportion of the HCW choosing to receive the second booster is 60%
 
• The expected monthly infection rate of 2.5% in the non-vaccinated group
 
• Expected monthly infection rate of 1.0% in the treatment group
 
• Median follow-up until switching to the booster administration in the non-vaccinated group (15%) of 4 months
 
• Type I error (<math>\alpha</math>) = 0.025 (one-sided)
 
• Log-rank test
 
• Enrollment period of 1 month
 
• Lost to follow-up of 10%
 
 
An evaluable sample size of 1000 subjects provides 80.0% power to reject the null hypothesis, signifying the booster strategy is superior to the comparison group at 6 months post-vaccination.

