STUDY PROCEDURES	
Screening and Enrollment
 
The following will take place at this visit:
 
 
• Confirmation of eligibility and informed consent will be signed.
 
• Demographics and medical history will be recorded.
 
• COVID-19 questionnaire regarding exposure and symptoms.
 
• Blood draw of three 5 ml vials, for antibody testing.
 
• Blood drawn for PBMC and antibody testing: 
 
◦ Will be ONLY at Soroka Medical Center.
 
◦ 150 subjects will be selected randomly. Subjects participating in this part will have 30 ml (3 vials of 9 ml and 1 vial of 3 ml) of blood drawn for PBMC and antibody testing. Others will have blood draw of three 5 ml vials, for antibody testing.
 
 
 
• A nasal and mouth swab will be performed for IgA, IgG and IgM levels testing
 
 
Visit 2 –6
 
 
• COVID-19 questionnaire regarding exposure and symptoms. Blood draw of 3 vials of 5 ml for antibody testing,
 
• Blood drawn for PBMC and antibody testing: 
 
◦ Will be ONLY at Soroka Medical Center. Subjects who were not part of the PBMC group and are willing to participate, will be asked again to sign informed consent.
 
◦ Subjects participating in this part will have 30 ml (3 vials of 9 ml and 1 vial of 3 ml) of blood drawn for PBMC and antibody testing. Others will have blood draw of three 5 ml vials, for antibody testing.
 
 
 
• A nasal and mouth swab will be performed for IgA, IgG and IgM levels testing
 
• Adverse events following vaccination and changes in medications (chronic and/or Immune suppression medication) will be collected
 

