#### **4      Background**

The SARS-CoV-2 virus causes severe respiratory illness and is an ongoing global pandemic. On December 12, 2020 the FDA approved Pfizer's BioNTech vaccine BNT162b2 which is a messenger RNA type of vaccine for use. This vaccine has shown in numerus studies the ability to induce a strong immune response and provide both humeral and cellular protection against wild type, alpha and delta variants of SARS-CoV2 virus. In Israel the national vaccine operation began in mid-December 2020 which included 2 initial doses three weeks apart. In August 2021 a first booster (3rd dose) was provided to enhance protection and due to reports of reduced immune response and clinical protection. Several studies have demonstrated that over time there is a decay in the antibody levels, and with them reduced protection.

Recently a new variant of concern has been identified (Omicron) and is causing a surge of infections worldwide. There is lack of knowledge regarding the effectiveness of the current schedule of vaccine against this new variant and whether a second booster (4th dose) will provide higher levels of clinical protection against this variant, currently the ministry of health is considering recommendations for a fourth dose for HCW.

The purpose of this study is to examine whether a fourth dose of vaccination will provide better protection against infection and clinical disease.

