## **5.8 Study Procedures**

### **5.8.1 Screening and Enrollment**

The following will take place at this visit:

- Confirmation of eligibility and informed consent will be signed.
- Demographics and medical history will be recorded.
- COVID-19 questionnaire regarding exposure and symptoms.
- Blood draw of three 5 ml vials, for antibody testing.
- Blood drawn for PBMC and antibody testing:
  - Will be at ONLY at Soroka Medical Center.
  - 150 subjects will be selected randomly. Subjects participating in this part will have 30 ml (3 vials of 9 ml and 1 vial of 3 ml) of blood drawn for PBMC and antibody testing. Others will have blood draw of three 5 ml vials, for antibody testing.
- A nasal and mouth swab will be performed.

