## 5.9 Laboratory testing

From each HCW at each visit the following tests will be performed:

- The Platelia SARS-CoV-2 Total Ab assay by Bio rad, is a semi-quantitative in vitro diagnostic test, in a one-step antigen capture format, for the detection of IgM/IgA/IgG antibodies to the SARS-CoV-2 in human serum and plasma (EDTA, heparin, ACD or citrate) specimens. This assay will be performed at SMC virology laboratory (head- [name]).
- Antibody profiling of blood and nasal and mouth samples will be tested using antigen microarrays, this will be performed by using chip antigen microarrays spotted with various coronavirus antigens, as well as antigens of other common respiratory pathogens. This assay will be performed at [name] laboratory at Ben-Gurion University of the Negev.
- On select samples from each visit neutralization assays for SARS-CoV-2 virus variants will be performed. Each sample selected will be tested for its ability to inhibit infection of target ACE2-expressing cells by reporter pseudoviruses that express the spike protein of either Delta or Omicron Variant of Concern. This assay will be performed at [name] laboratory at Ben-Gurion University of the Negev.
- Blood samples for PBMC'S will be stored at [name] laboratory at Ben-Gurion University of the Negev for future research.

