## 6 Statistical Considerations and Analysis Plan

In this prospective observational registry we aim to assess the rates of the COVID-19 infection as confirmed by PCR testing or positive serology for N antigen during the follow up period. We hypothesize that booster of BNT162b2 vaccine in healthcare workers (HCW) will lower the rates of the COVID-19 infection as compared to HCW choosing not to receive the second booster.

We aim to enroll up to 1000 subjects. The following assumptions were used to estimate the power of the analysis.

- The proportion of the HCW choosing to receive the second booster is 60%
- The expected monthly infection rate of 2.5% in the non-vaccinated group
- Expected monthly infection rate of 1.0% in the treatment group
- Median follow-up until switching to the booster administration in the non-vaccinated group (15%) of 4 months
- Type I error ( $\alpha$ ) = 0.025 (one-sided)
- Log-rank test
- Enrollment period of 1 month
- Lost to follow-up of 10%

An evaluable sample size of 1000 subjects provides 80.0% power to reject the null hypothesis, signifying the booster strategy is superior to the comparison group at 6 months post-vaccination.

All statistical analyses will be performed using Statistical Analysis System (SAS) for Windows (version 9.4 or higher, SAS Institute Inc. Cary, NC) or other widely accepted statistical or graphical software. In general, data for all study patients will be combined and presented. Individual data will be presented in patient listings.

Descriptive statistics will be used to present the data and to summarize the results. Categorical variables will be presented using frequency distributions and cross tabulations with numbers and percent per group. Continuous variables will be summarized by presenting the number of observations (N), mean, 95% confidence interval of the mean, standard deviation, median, minimum, and maximum values.

The primary outcome will be analyzed within the paradigm of the survival analysis, i.e. log-rank test for the univariate analysis. Since it is possible that those who chose not to be vaccinated will differ in a number of characteristics, we will utilize Cox regression models with time dependent variable (timing of the booster) with the adjustment for the potential confounders. The confounders will be identified by the DAG approach. In addition different approaches to approximate the counterfactual world assumption such as propensity score adjustment will be considered.

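### Unrecognised infections that have not yet seroconverted at consent pass both entry checks and then count as primary events, because no event is required to begin after entry

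*Protocol*

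**What the plan says.** Two rules in the Protocol keep infected workers out. Section 5.5.2 excludes anyone with "History of COVID-19 infection". Section 5.5.3 acts on the enrolment blood sample: "Discontinuation in the study will be if the antibody result at enrollment visit shows the participant already had the disease".

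Nothing else at enrolment tests for infection. Section 5.9 describes a total-antibody assay "for the detection of IgM/IgA/IgG antibodies to the SARS-CoV-2 in human serum and plasma". The swab is also an antibody sample; the Protocol Summary says "A nasal and mouth swab will be performed for IgA, IgG and IgM levels testing". The schedule in section 5.3 lists no PCR at any visit. Section 5.8.1 has a "COVID-19 questionnaire regarding exposure and symptoms", but no eligibility or counting rule uses the answers.

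The primary outcome is "COVID-19 infection as confirmed by PCR testing or positive serology for N antigen during the follow up period". Section 5.10 runs participation for 6 months from consent and expects enrolment to take one month. Nothing requires the infection to have begun after entry, and no early period is set aside.

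The Background gives the setting: "Recently a new variant of concern has been identified (Omicron) and is causing a surge of infections worldwide". Section 6 treats boosting as the worker's own choice.

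**The concern.** A worker infected shortly before consent, not tested and not yet seroconverted, has no history to report and a negative enrolment antibody result. A PCR some days later, or N serology at Month 1, then makes this worker a primary event although the infection preceded entry.

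The booster cannot have prevented such an infection if the dose came after it. Spread evenly over the groups, these cases dilute the effect. The groups are self-selected, however, and workers who feel unwell or know of an exposure may put off the booster. The cases would then gather in unboosted time and push the estimate towards protection. Delaying the count only in boosted time, for example by a lag after the dose, would leave them in the control group. With enrolment squeezed into about one month of a surge, infection prevalence at entry matters more than it would with long accrual.

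**Working it through.** **The plan's own figure.** The one computed figure is 80.0% power. With hazards derived from 2.5% and 1.0% per month, 6 months, one-sided 0.025 and a 60/40 split, 1000 subjects with 10% loss give 81.3% if the median time to switching is 4 months and switchers stay in the control group. Under that treatment of switchers, other choices of sample size and loss give 77–83%. The other one-sided readings tried at 6 months give 94% or more. The power figure does not settle this point, but its inputs supply the rates below.

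**Inputs from section 6.** 400 unboosted at 2.5% per month, 600 boosted at 1.0% per month, 6 months.

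**Assumptions, not in the documents.** The antibody-negative window is 7, 14 or 21 days. The 2.5% rate applies to all 1000 subjects just before entry, so nobody is yet protected by the fourth dose in that window. No carried-in case is known at consent.

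**True events, no loss or switching.**
- Control: 400 × (1 − e^−0.15) = 55.7 over 55.7/0.025 = 2229 person-months.
- Boosted: 600 × (1 − e^−0.06) = 34.9 over 34.9/0.010 = 3494 person-months.
- Total about 91. With 10% loss and 15% switching by 4 months the total is 47.8 + 33.3 + 2.4 = 83.5.

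**Carried-in cases.** 1000 × 0.025 × 14/30.4 = 11.5; 5.8 at 7 days and 17.3 at 21 days.

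**Rate ratios at 14 days.**
- Even spread (6.9 boosted, 4.6 control): ((34.9 + 6.9)/3494) / ((55.7 + 4.6)/2229) = 0.44.
- Controls twice as likely per head: 400 × 2x + 600 × x = 11.5, so x = 0.0082, giving 6.6 control and 4.9 boosted. ((34.9 + 4.9)/3494) / ((55.7 + 6.6)/2229) = 0.41.
- The same imbalance with no true effect: the boosted group has 600 × (1 − e^−0.15) = 83.6 events over 3343 person-months. ((83.6 + 4.9)/3343) / ((55.7 + 6.6)/2229) = 0.95.
- All in controls: 0.0100 / ((55.7 + 11.5)/2229) = 0.33. With no true effect: 0.025 / ((55.7 + 11.5)/2229) = 0.83.

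| Window | Carried in | Even, true 0.40 | All in controls, true 0.40 | All in controls, no effect |
|---|---|---|---|---|
| 7 days | 5.8 | 0.42 | 0.36 | 0.91 |
| 14 days | 11.5 | 0.44 | 0.33 | 0.83 |
| 21 days | 17.3 | 0.46 | 0.31 | 0.76 |

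**Cross-check.** With 10% loss, 15% switching by 4 months and switchers counted as boosted (section 5.4), even spread moves the hazard ratio from 0.397 to 0.428 if 1% are carried in and to 0.455 if 2% are. Power stays at 97–98%.

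**The case against.** A counting start and sensitivity analyses often sit in a SAP, and none is shown. If that SAP already sets a common start, the point is met. But eligibility, the primary event and follow-up from consent are fixed in the protocol, and as written they admit these events.

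A reader might infer that the antibody check is blind to recent infection. The documents do not support that. The assay covers IgM, IgA and IgG, so a recent infection that has already seroconverted can be caught. Only the interval before seroconversion is missed, and the documents do not give its length.

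A reader might also infer that the design manufactures 9–24% protection where there is none. That needs every carried-in case to be an unboosted control and none to be known at consent. The mechanism also partly undercuts itself: a worker with a recognised infection is excluded, a silent infection gives little reason to defer a booster, and an ill or isolating worker may postpone the study visit too. What remains is the worker with an exposure or mild symptoms and no test. A twofold imbalance leaves the assumed effect almost unchanged.

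Section 6 plans confounder adjustment, and enrolment exposure and symptoms are available as covariates. That may reduce an imbalance between groups. It does not turn an infection acquired before entry into one acquired in follow-up, so the dilution stays.

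**Conclusion.** The gap is real and its effect is small to moderate. Under the stated assumptions about 6 to 17 per 1000 subjects are carried in, against roughly 83 to 91 true events. There would be fewer if some are already known by test at consent, and more, in proportion, if the rate at enrolment exceeds 2.5% per month. Even spread is the neutral case and is conservative (0.42–0.46 instead of 0.40). The direction can reverse if carried-in cases are commoner among the unboosted. All in controls is a bound, not an expectation. Neither the window nor the imbalance can be read from the documents. This is a cheap improvement to a rule the protocol itself fixes, not a flaw that undermines the comparison.

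**What to change.** In section 6 and in the primary outcome definition, start at-risk time for the primary outcome on the same prespecified day after enrolment in both groups, for example day 7 or day 14. Subjects PCR-positive before that day are not in the risk set.

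Add two prespecified sensitivity analyses: (a) drop serology-only positives first seen at Month 1, since the counting-start day does not remove these; (b) drop subjects who reported COVID-19 symptoms or exposure on the enrolment questionnaire.

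Deferring or re-screening exposed workers is not proposed. It would add visits within a one-month enrolment period and remove highly exposed staff, who are part of the population of interest.

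Cost: wording only, with no new test or visit. A day-14 start gives up 14/30.4/6, about 8%, of follow-up. It loses at most about 400 × 0.025 × 0.46 + 600 × 0.010 × 0.46 = 4.6 + 2.8, or about 7, true early events; a day-7 start loses about half of that.

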#### **5.6 Enrollment**

Prior to participation in this study, the Investigator must obtain written approvals from the ethics committee and other local regulatory bodies as appropriate approval for the protocol and the informed consent form. Failure to obtain a signed and hand dated informed consent prior to the procedure constitutes a protocol violation, which is reportable to the EC.

The Investigator will obtain an approval from the ethics committee to recruit and sign participants on informed consent form by study research members (such as study coordinators, research assistant, study investigator and etc.) with GCP certificate.

#### **5.7 Subject Screening**

Screening will be performed at each participating medical center; an email or other medical communication will be sent out to the employees of each participating medical center with a short description of the study and invite them to learn more of the study and be screened.

HCW who fulfills all the inclusions and none of the exclusion criteria will be approached and offered participation in the study by a study research member. A study research member will explain the purpose, procedures and intent of the study to each potential

participant. Interested HCW will be asked to provide written consent prior to performing any study procedure.

## **5.8 Study Procedures**

### **5.8.1 Screening and Enrollment**

The following will take place at this visit:

- Confirmation of eligibility and informed consent will be signed.
- Demographics and medical history will be recorded.
- COVID-19 questionnaire regarding exposure and symptoms.
- Blood draw of three 5 ml vials, for antibody testing.
- Blood drawn for PBMC and antibody testing:
  - Will be at ONLY at Soroka Medical Center.
  - 150 subjects will be selected randomly. Subjects participating in this part will have 30 ml (3 vials of 9 ml and 1 vial of 3 ml) of blood drawn for PBMC and antibody testing. Others will have blood draw of three 5 ml vials, for antibody testing.
- A nasal and mouth swab will be performed.

### **5.8.2 Visit 2 –6**

- COVID-19 questionnaire regarding exposure and symptoms. Blood draw of three vials of 5 ml for antibody testing,
- Blood drawn for PBMC and antibody testing:
  - Will be at ONLY at Soroka Medical Center. Subjects who were not part of the PBMC group and are willing to participate, will be asked again to sign informed consent.
  - Subjects participating in this part will have 30 ml (3 vials of 9 ml and 1 vial of 3 ml) of blood drawn for PBMC and antibody testing. Others will have blood draw of three 5 ml vials, for antibody testing.
- A nasal and mouth swab will be performed.
- Adverse events following vaccination and changes in medications (chronic and/or Immune suppression medication) will be collected

## 5.9 Laboratory testing

From each HCW at each visit the following tests will be performed:

- The Platelia SARS-CoV-2 Total Ab assay by Bio rad, is a semi-quantitative in vitro diagnostic test, in a one-step antigen capture format, for the detection of IgM/IgA/IgG antibodies to the SARS-CoV-2 in human serum and plasma (EDTA, heparin, ACD or citrate) specimens. This assay will be performed at SMC virology laboratory (head- [name]).
- Antibody profiling of blood and nasal and mouth samples will be tested using antigen microarrays, this will be performed by using chip antigen microarrays spotted with various coronavirus antigens, as well as antigens of other common respiratory pathogens. This assay will be performed at [name] laboratory at Ben-Gurion University of the Negev.
- On select samples from each visit neutralization assays for SARS-CoV-2 virus variants will be performed. Each sample selected will be tested for its ability to inhibit infection of target ACE2-expressing cells by reporter pseudoviruses that express the spike protein of either Delta or Omicron Variant of Concern. This assay will be performed at [name] laboratory at Ben-Gurion University of the Negev.
- Blood samples for PBMC'S will be stored at [name] laboratory at Ben-Gurion University of the Negev for future research.

